6.2.3 Follow-up (Postoperative Days 4-7)

During this time, opioid consumption and caffeine intake assessments will be obtained over the telephone. Adverse events will continue to be monitored.

SCHEDULE OF ACTIVITIES

	Screen	Visit 1 Day 1	Visit 2 Day 2	Visit 3 Day 3	Visit 4 Day 4	Phone call Days 5-7	Day 30
Protocol Activity		Day of Surgery	POD1	POD2	POD3	POD4-7	
Visit (POD1-3) /Phone call (POD4-7)	-	X	X	X	X	X	
Informed consent	X						
Medical history	X						
Vitals*	X	X	X	X	X		
Depression, Anxiety, and Affect Scales	X			X			
Serum pregnancy test		X					
Randomization		X					
Treatment with study agent		X					
Opioid use assessments		X	X	X	X	X	
Cognitive function testing	X	X^{\dagger}					
Pain/sleep assessments [‡]	X	X	X	X	X		
Caffeine intake assessment	X		X	X	X	X	
EEG assessments		X			·		
Adverse event assessment	_	X	X	X	X	X	
Health and well-being survey							X

^{*} Vitals will be recorded per clinical protocol on each respective ward/ICU. †Second cognitive function testing session will occur in the postanesthesia care unit ‡Pain and sleep assessments will occur and twice daily (morning and afternoon) from POD1-3; the RCSQ in particular will be administered on Day 1, preoperatively. Pain assessments will also be taken once in the postanesthesia care unit prior to the cognitive function assessment. POD = postoperative day, TMT = trail making test, EEG = electroencephalogram

7 ASSESSMENTS

7.1 Primary Endpoint Assessments

Cumulative opioid consumption (mg) – through first three postoperative days

7.2 Secondary and Tertiary Assessments

Secondary Outcomes

- •VAS scores (n)
- •BPS scores (n)
- •Time to anesthetic emergence (min)
- •Change in TMT scores (n)
- •Delirium incidence (%)
- •Postoperative depression screen incidence (%)
- •Postoperative anxiety screen incidence (%)
- •Change in affect scores (n)

Tertiary Outcomes

- •EEG spectral power (decibels, dB)
- •EEG connectivity (e.g., phase lag index, PLI)
- •Daily number of caffeinated beverages (n) to compare overall caffeine intake between the two groups throughout the study period (as a potential confounding/mediating variable).
- •Preoperative sleep quality, via Richards-Campbell Sleep Questionnaire (continuous measure, n) as a potential confounding/mediating variable.

- •New self-reported sleep disturbances (n) in each group
- •Opioid use (mg), postoperative days 4-7
- •Opioid use (yes/no) at 30 days
- •Patients-reported health and well-being scores (n) Veterans RAND 12 Item Health Survey (VR-12, continuous measure)⁵² at 30 days

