Yucel et al., 1999:²⁹ prospective, double-blinded randomized trial (N=30, caffeine arm) conducted with orthopedic surgery patients. 500 mg caffeine-sodium benzoate (250 mg caffeine) infused over 90 minutes, significant improvement in post-spinal headache. No adverse events or side effects were reported.

Weber et al. 1997:³⁰ this prospective, randomized, double-blinded trial examined caffeine efficacy in relation to postoperative headache and recovery time. Caffeine was found to significantly reduce postoperative headache compared to placebo (10% vs. 23%, respectively, p<0.05) in patients at risk for withdrawal symptoms.

Camann et al., 1990:³¹ prospective, double-blinded, randomized trial (N=20, caffeine arm) conducted with postpartum patients. Oral formulation of caffeine (300 mg). Significant improvement noted in spinal headaches. No significant side effects reported with caffeine therapy. 1/20 patients (5%) complained of mild/transient flushing and jitteriness after receiving caffeine, though this was the same proportion in the placebo group (5%).

Jarvis et al., 1986: 32 exploratory study, letter to the editor (N=18) – 500 mg caffeine-sodium benzoate (250 mg caffeine) infused over 60 minutes, second dose if necessary. Significant relief in 14/18 (75%) of patients. No adverse events or significant side effects were reported.

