Inclusion criteria: Adult (≥18 years old) patients undergoing non-cardiac, non-neurologic, non-major vascular surgery (i.e., below the diaphragm).

Exclusion criteria: Emergency surgery, cognitive impairment precluding capacity for informed consent, uncontrolled cardiac arrhythmias, seizure disorders, intolerance or allergy to caffeine, history of diabetes, preoperative opioid use, pheochromocytoma, acute liver failure, enrolled in conflicting research study, pregnancy, breastfeeding, severe visual or auditory impairment (may hinder cognitive function testing), and patients unable to speak English.

Perioperative and anesthetic procedures: Patients will be consented and enrolled at preoperative clinic locations, where a medical and psychiatric history will be taken and baseline assessments will be administered (described further below). After enrollment, patients will also complete a caffeine intake survey to quantify baseline caffeine consumption. On the day of surgery, baseline cognitive function testing (TMT) will take place in the preoperative holding area. Subsequently a 16-channel wireless EEG system (Cognionics, Inc.) will be applied to the scalp for continuous monitoring during surgery and the perioperative period. Once in the operating room, anesthetic induction and maintenance will proceed as deemed clinically appropriate by the anesthesia team. At the beginning of surgical closure, the study drug will be given via intravenous infusion over 60 minutes (placebo vs. caffeine, 200 mg) in a triple-blinded fashion: the anesthetic team, research staff, and patient will all be blinded to the intervention. Infusion of this dose over a 60-minute period has been safely described, without significant side effects or adverse events noted.^{28,32} A member of the research team will remain in the operating room to monitor drug infusion and collect data regarding timing of anesthetic discontinuation and emergence; this will aid methodological rigor and data validation for the study. The EEG sensors will remain in place during the operation and emergence from anesthesia; they will then be removed shortly after PACU arrival. One hour after the caffeine infusion finishes, pain and cognitive function measures will be assessed.

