6 STUDY PROCEDURES

6.1 Screening Visit

For initial screening visits, patients will be seen during preoperative clinic visits. The study coordinator will review the study details with potential participants, and informed consent will be obtained after confirming eligibility criteria are met. Depending on when a preoperative clinic visit is scheduled in relation to surgery, the timeframe from enrollment to drug administration may vary significantly (days-to-weeks). The goal will be to recruit patients whose surgeries are scheduled for the morning, so as to minimize the likelihood of administering caffeine late in the afternoon. See "Schedule of Activities" for full list of procedures that will occur at this visit and all subsequent visits. Assessments, testing, and measures are described in detail in the above "Study Design" section.

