6.2 Treatment Study Period

6.2.1 Visit 1 (Day 1)

As outlined in the above protocol, visit 1 (day 1) will be the day of scheduled surgery. During this time, a preoperative pregnancy test will first be drawn as clinically indicated. Vitals will be taken throughout the perioperative period per clinical guidelines and protocols. The RCSQ will be administered to assess sleep quality the prior evening. Baseline Trail Making Test (TMT) scores will be collected. The wireless EEG cap will then be placed preoperatively, and EEG monitoring will then commence perioperatively under supervision of the study team. A member of the study team will then receive the study drug from the research pharmacy, which will prepare the drug per block randomization protocol. The study team will then administer this during (one-hour infusion) at the beginning of surgical closure. The EEG cap will be removed after postanesthesia care unit (PACU) arrival, and one hour after the infusion has finished, the study team will perform the designated research study assessments (i.e., pain assessments, cognitive function testing, and Quality of Recovery (QoR) questionnaire). Intraoperative and PACU opioid data will also be tabulated.

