6.2.2 Visits 2 – 4 (Postoperative Days 1-3)

Morning and afternoon pain (VAS, BPS), delirium, sleep disturbance, and caffeine intake assessments will be taken. Opioid consumption will be calculated during this time, and adverse events will also be recorded. Vitals will be recorded per clinical protocol on each respective ward/ICU. On postoperative day one, QoR will be collected. On postoperative day three, follow-up inpatient HADS and PANAS assessments will take place to assess depression, anxiety, and affect.

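### Sections 7.2 and 9.2.2 together allow adjustment for caffeine intake after the infusion, while intake on the day of surgery is not collected

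*Combined protocol and SAP*

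**What the plan says.** Three parts of the combined protocol and SAP bear on this.

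- **Role of intake.** Among the tertiary outcomes, section 7.2 gives the daily number of caffeinated drinks, to "compare overall caffeine intake between the two groups throughout the study period (as a potential confounding/mediating variable". The synopsis also lists caffeine use around the time of surgery among the study variables.
- **Collection.** Section 3: "After enrollment, patients will also complete a caffeine intake survey to quantify baseline caffeine consumption". Section 6.1 adds that "the timeframe from enrollment to drug administration may vary significantly (days-to-weeks". For postoperative days 1-3, section 6.2.2 says "Morning and afternoon pain (VAS, BPS), delirium, sleep disturbance, and caffeine intake assessments will be taken". For days 4-7, section 6.2.3 says "opioid consumption and caffeine intake assessments will be obtained over the telephone". In the Schedule of Activities, the row "Caffeine intake assessment" is marked at screening, POD1, POD2, POD3 and POD4-7. The day-of-surgery cell is empty. The Visit 1 text in 6.2.1 has no caffeine question, although it does ask about the night before: "The RCSQ will be administered to assess sleep quality the prior evening".
- **Use in models.** Section 9.2.2 compares demographics, confounders and relevant predictors by caffeine group and by day, and puts those with a standardised difference above 0.1 into the multivariable models. It does not say that these must be baseline measures. Section 9.2.3 names group, time, demographic and intraoperative terms. Section 3 stratifies randomisation by age and gender. Neither section names caffeine intake.

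**The concern.** A confounder of a randomised comparison has to precede allocation. Coffee drunk on POD1-7 comes after the infusion. It may be a consequence of the infusion or a step on the way to the outcome, but it cannot confound. A plan that labels it a possible confounder, and elsewhere adjusts for imbalanced confounders without regard to timing, lets an analyst who follows the text condition on something the treatment may have changed. The resulting coefficient no longer estimates the total effect of caffeine on opioid consumption.

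The second issue is smaller. In a trial of caffeine, the measure closest to the infusion (how much caffeine was taken recently, and when) is not recorded. Wording that implies coverage of the whole study period is not matched by any procedure on Day 1.

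**Working it through.** The plan gives no figure on this point to reproduce. The check compares sections, followed by one probability and one identity.

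**1. When intake is recorded**

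| Time | Schedule row | Text |
|---|---|---|
| Screening | marked | section 3, survey after enrolment |
| Day of surgery | empty | 6.2.1, no caffeine question |
| POD1-3 | marked each day | 6.2.2 |
| POD4-7 | marked | 6.2.3, telephone |

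The schedule and the visit text agree that nothing is collected on Day 1, so the empty cell is not a table-extraction fault. The only value before the infusion is the screening survey, taken days to weeks ahead. Everything else that feeds the 7.2 variable follows the infusion.

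**2. Route into the models**

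- 7.2 labels the variable as possibly confounding.
- 9.2.2 examines confounders by group and by day, and includes those whose standardised difference exceeds 0.1.
- No section excludes measures taken after randomisation.

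**3. How often the 0.1 threshold is passed by chance**

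Inputs: 30 per arm (Figure 2; also 60 in section 9.1 at 1:1 allocation) and the 0.1 threshold (9.2.2). Assumptions: a continuous covariate unaffected by treatment, and a normal approximation.

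- Standard error of the standardised difference: √(2/n) = √(2/30) = 0.258.
- Threshold in standard errors: 0.1/0.258 = 0.387.
- P(|difference| > 0.1) = 2 × [1 − Φ(0.387)] = 2 × 0.349 = 0.70.

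Section 9.1 also mentions 71 recruited patients. With 35 per arm: √(2/35) = 0.239, 0.1/0.239 = 0.418, and 2 × [1 − Φ(0.418)] = 0.68. The answer hardly changes. This probability is at its lowest when the true difference is zero, so a variable that the infusion does shift would pass more often.

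**4. What adjustment does**

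For the linear regression of cumulative opioid consumption in 9.2.3, let *a* be the caffeine-minus-placebo difference in intake after the infusion, and *b* the within-arm slope of opioid consumption on that intake (taken as common to both arms). Then

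adjusted group coefficient = unadjusted group coefficient − *a* × *b*.

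The unadjusted coefficient is unbiased for the total effect under randomisation. If the infusion does not change later intake, the true *a* is zero and adjustment brings no systematic error. If it does, and intake is related to opioid use within arms, the adjusted coefficient is biased for the total effect. The documents give neither *a* nor *b*, so the size and sign of that bias cannot be stated.

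**The case against.** The strongest reply is that no section commits to adjusting the primary model for postoperative intake. Section 9.2.3 adds only demographic and intraoperative variables, 7.2 says mediating as well as confounding and speaks of a comparison between groups, and 9.1 foresees mediator analyses. The mediator role is legitimate. It is also true that the 9.2.2 rule could bring in screening intake if that were imbalanced. What remains is that 9.2.2, read with 7.2, permits the adjustment and nothing forbids it. The harm is conditional, and preventing it costs only wording.

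Three stronger readings are tempting, and the documents do not support them.

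- **That the missing Day 1 question biases the primary comparison.** Randomisation balances caffeine intake before the infusion in expectation. The screening survey also covers habitual use, which is the natural proxy for withdrawal risk. Only recent intake and time since last caffeine are missing, and the aim in 6.1 of recruiting morning cases narrows the window for same-day intake.
- **That the trial must separate withdrawal relief from analgesia.** Section 1.4 does report a benefit "in patients at risk for withdrawal symptoms", but the outcome was postoperative headache (10% vs. 23%), not opioid consumption. The hypothesis in 1.3 does not require an effect apart from withdrawal relief, and a net effect in a mix of users is a fair target.
- **That unrecorded caffeine costs a calculable amount of power.** The documents give no share of patients affected. Withdrawal in the placebo arm could enlarge the difference rather than shrink it. Asking about intake would not remove any dilution.

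**Conclusion.** The point holds in two parts of unequal weight.

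First, and more important, 7.2 and 9.2.2 together allow adjustment for caffeine intake after the infusion. Such a variable passes the 0.1 threshold about 70% of the time at 30 per arm even with no treatment effect on it. Adjustment biases the total effect if the infusion alters later intake and intake is related to opioid use within arms. Both conditions are plausible, but neither is quantified in the documents. The 70% describes how easily the variable enters a model; it is not the size of any bias.

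Second, recent caffeine intake on the day of surgery is not recorded, and the synopsis and 7.2 do not match the schedule. The loss is in precision, in checking for chance imbalance and in interpretation. The randomised primary comparison stays valid, and no power loss can be attached to the gap.

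**What to change.** 1. In 7.2, drop the confounding label for postoperative intake and report it only as an outcome or mediator. In 9.2.2, restrict the standardised-difference rule to measures taken before randomisation, and state that postoperative caffeine intake does not enter any model used to estimate the treatment effect. This is a wording change with no other cost.
2. Add the existing caffeine intake assessment to Visit 1, before the infusion and alongside the RCSQ: amount in the previous 24 hours and time of last intake. Mark the Day 1 cell and add the item to 6.2.1, so that both agree with the synopsis and 7.2. The cost is two questions at a contact that already takes place. Self-report remains a proxy for caffeine on board.
3. Prespecify the screening intake already collected as a baseline covariate in the primary model, instead of leaving its entry to an observed imbalance. With the Visit 1 measure, if that is used too, this takes one or two degrees of freedom.

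An estimate of treatment effect by habitual intake is optional. If reported, it should be labelled exploratory and given with its interval, which will be wide at this sample size.

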1.2 Background and Rationale

Over 300 million surgical procedures are performed each year worldwide, 9 the majority with general anesthesia. Many fundamental questions in the fields of neuroscience and anesthesiology persist, such as the relationship between pain and arousal state perturbations. Evidence suggests a neurobiologic pain-arousal state connection, such that pain, sleep disturbance, and cognitive dysfunction may interact in a synergistic, reciprocating manner (Figure 1).^{4,10-13} In clinical practice, these adverse pain-arousal state interactions are often ineffectively addressed, and surgical patients are particularly vulnerable to entering this refractory cycle given the pain and brain state alterations associated with surgical interventions. In fact, 75% of surgical patients report moderate-to-severe pain after surgery, 1 nearly 50% of patients report sleep disturbances perioperatively, 13 and up to 70% of patients experience cognitive dysfunction after surgery. 14,15 Acute postoperative pain and cognitive dysfunction are also associated with negative outcomes, such as increased hospital length of stay, ¹⁶ persistent opioid use, ⁸ and prolonged cognitive decline. ^{17,18} Opioids remain a mainstay therapy for treating acute surgical pain, but opioids also interfere with sleep architecture^{6,7} and cognitive function, ^{5,19,20} further propagating the deleterious cycle of painarousal state perturbation (Figure 1).

Figure 1: Sleep disturbance, pain, and cognitive dysfunction are reciprocally related.

Preliminary data from our laboratory research group demonstrate that caffeine, a non-selective adenosine receptor antagonist, demonstrates both acute anti-nociceptive properties and protection against postoperative pain in both sleep-deprived and non-sleep-deprived rat models.²¹ In fact, recent systematic reviews found that caffeine provided significant analgesic benefit as part of a multimodal strategy in both surgical²² and non-surgical settings.²³ Caffeine also augments electroencephalographic (EEG) signs of arousal,²⁴ and it has been shown to improve cognitive function in a variety of settings.²⁵ Nonetheless, caffeine is not routinely given perioperatively, and whether caffeine facilitates such neurocognitive arousal after surgery, and how such brain state modulation may impact postoperative pain and opioid requirements, remains unknown.

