3 STUDY DESIGN

This will be a single-center, triple-blinded, randomized controlled trial at the University of Michigan Health System, and approval has been obtained from the University Michigan Medical School IRB. The overall study flow is presented in the CONSORT⁴¹ Flow Diagram (Figure 2). As with our past studies, patients will be recruited at preoperative clinics, where informed consent will be obtained. Randomization methods will follow a stratified randomization model to match patients based on age and gender. Participants will be randomized with a 1:1 allocation ratio (placebo: caffeine) in a two-arm parallel design, and the randomization schedule and coding will be held by our hospital research pharmacy. Prepared intravenous piggyback solutions of 5% dextrose in water or caffeine citrate (200 mg caffeine) will be directly delivered to the operating room prior to the surgery of enrolled participants. The dose of 200 mg was chosen for two reasons: (1) this dose is in-line with similar clinical neurophysiology studies involving caffeine^{34,35,42,43} and (2) this has been the intraoperative dose used for safely preventing post-dural puncture/post-operative pain in surgical and obstetric patients. ^{22,29,32} In these studies, no significant side effects or adverse events were reported in relation to caffeine. This study will fulfill CONSORT guidelines⁴¹ for clinical trials as outlined in the following sections. Furthermore, this trial will be registered with www.clinicaltrials.gov prior to trial initiation, and all study team members will be certified in Good Clinical Practice as outlined by the NIH.

Assessment for **Enrollment** eligibility **Exclusions** Randomization Allocation Allocation to placebo (n=30) Allocation to caffeine (n=30) Analysis Analysis Anesthetic emergence time ◆ Anesthetic emergence time ◆ EEG power and connectivity · EEG power and connectivity ◆ Trail Making Test ◆ Trail Making Test · Postoperative opioid use Postoperative opioid use • Postoperative pain assessments · Postoperative pain assessments Delirium assessments · Delirium assessments Depression, anxiety scales • Depression, anxiety scales ◆ Affect questionnaire ◆ Affect questionnaire ◆ 30-day follow-up health survey ◆ 30-day follow-up health survey

Figure 2: Planned study flow diagram based on Consolidated Standards of Reporting Trials (CONSORT)

Planned study flow diagram based on Consolidated Standards of Reporting Trials (CONSORT).⁴¹ EEG = electroencephalogram

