Pain and sleep assessments: Inpatient opioid consumption will be monitored from the first PACU assessment through postoperative day three (or discharge, whichever occurs sooner) (primary outcome). Subacute opioid consumption (postoperative days 4-7) will be calculated as an additional outcome. All opioids will be converted to oral morphine equivalents (mg), and intraoperative opioid administration will be calculated as well and compared between groups. Pain measures will include the 10 centimeter Visual Analog Scale (VAS)⁴⁴ and Behavioral Pain Scale (BPS)⁴⁵ for subjective and objective pain assessment, respectively. Assessments will begin 1 hour after caffeine infusion has finished (once patient is in the PACU), and they will continue twice daily (morning and afternoon) for the first three postoperative days. Preoperatively, the Richards-Campbell Sleep Questionnaire (RCSQ)⁴⁶ will be administered to determine self-reported sleep quality the previous evening. As an additional outcome, self-reported sleep disturbances will also be assessed during these daily pain assessments (i.e., from the PACU through postoperative day 3).

EEG data acquisition: Our research group has extensive experience with EEG data acquisition and analysis in human volunteers^{47,48} and surgical patients.^{49,50} We have

demonstrated feasibility with collecting whole-scalp, 16-channel wireless EEG data (Cognionics, Inc.) in 50 surgical patients. Representative spectral and connectivity data are presented in Figure 3. Our group will use this same EEG technology to collect and analyze data for the proposed study. Spectral power (decibels, DB) and connectivity (phase lag index, PLI) data will be collected and analyzed during anesthetic emergence and PACU arrival.

[figure not shown]

Figure 3: Representative wireless EEG data from a surgical patient

Example wireless perioperative EEG data obtained from a related study (R01GM098578). LOC = loss of consciousness, PACU = postanesthesia care unit, dB = decibels, PLI = phase lag index (an EEG measure of functional connectivity).

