9 DATA ANALYSIS/STATISTICAL METHODS

9.1 Sample Size Determination

Sample size and power analysis is based on opioid consumption data observed in 102 hysterectomy patients treated at the University of Michigan with patient heterogeneity with respect to CNS involvement in the pain processing summarized by the Fibromialgia Survey score (FM). Acute opioid responses on POD1 varied between 0.7 and 6.5 (mean OME) with the standard deviation varying 3-18, dependent on the tertile of the FM score. Based on these data we hypothesize that caffeine affecting the pain processing system can show a difference as large as 0.7 vs. 6.5 with standard deviations of 3 and 10, respectively. This will give us the power of 83%, with a sample size of 60, to detect the difference by a two-sided ttest with unequal variances. We note that the opioid consumption distribution is of exponential type and therefore sample means, while approximately normal are a rather crude summary of the difference in the OME distribution by group. We therefore consider the above calculation conservative. The expected reserves of power attained through the use of the appropriate longitudinal model (see Analysis of Primary Endpoint) will be used to lend more power to secondary regression and causal analyses involving explanatory variables and potential mediators. We expect a ~10% drop-out rate, and will continue recruitment until the full 71 patients have been recruited (after drop-out).

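### Preoperative sleep quality (RCSQ) is listed as a tertiary outcome and possible mediator although it is measured before the drug, and its use as a covariate is left to chance imbalance

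*Combined protocol and SAP*

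**What the plan says.** Section 7.2, under tertiary outcomes, lists "Preoperative sleep quality, via Richards-Campbell Sleep Questionnaire (continuous measure, n) as a potential confounding/mediating variable". The line before it, on daily caffeinated beverages, carries the same confounding/mediating label. New self-reported sleep disturbances, assessed after surgery, are a separate item in that list.

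Three places fix the timing of the RCSQ. Section 3 says it "will be administered to determine self-reported sleep quality the previous evening". Section 6.2.1, on the day of surgery, says "The RCSQ will be administered to assess sleep quality the prior evening". The footnote to the Schedule of Activities says "the RCSQ in particular will be administered on Day 1, preoperatively". For the drug, Section 3 says: "At the beginning of surgical closure, the study drug will be given via intravenous infusion over 60 minutes".

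On analysis, Section 9.1 foresees "secondary regression and causal analyses involving explanatory variables and potential mediators" but names no mediator. Section 9.2.2 admits confounders and predictors to the multivariable models when their standardised difference exceeds 0.1. Section 9.2.3 adds demographic variables to the model and then intraoperative factors; preoperative sleep is in neither set.

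**The concern.** A mediator must be something the treatment can change. A score describing the night before surgery is settled before any caffeine is infused, so it can be neither an outcome of the drug nor a step on its causal path. Section 7.2 nevertheless gives it the mediator label, Section 9.1 announces analyses of unnamed mediators, and an analyst could reasonably connect the two. A positive result would then be reported as mechanism when it could only be chance.

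The second issue is the use that is valid. Section 1.2 ties sleep closely to pain, so preoperative sleep is a plausible prognostic covariate for opioid use. Its only written route into a model is the imbalance rule, which is applied once the data are in and takes no account of whether the variable predicts the outcome.

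**Working it through.** **1. Order of events.** The RCSQ refers to the previous night and is completed preoperatively on Day 1. The drug starts at the beginning of closure. The Schedule also puts randomisation on Day 1 without giving its order relative to the RCSQ. This does not matter: no drug has been given, and patient and research staff are blinded. With allocation intact ("Participants will be randomized with a 1:1 allocation ratio (placebo: caffeine) in a two-arm parallel design"), the true arm difference in RCSQ is 0, and so is the true indirect effect through it.

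**2. The plan's own power figure.** Inputs from Section 9.1: means 0.7 and 6.5, SDs 3 and 10, 60 patients (30 per arm in Figure 2), two-sided unequal-variance t-test. Alpha is not stated; 0.05 is assumed.
- SE = sqrt(9/30 + 100/30) = 1.906, with Satterthwaite df 34.2.
- Noncentrality = 5.8/1.906 = 3.04.
- Power = 84.0%, against the stated 83%. The figure reproduces closely, and nothing below changes it.

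**3. Chance imbalance.**
- SE of the standardised difference = sqrt(2/30) = 0.258, so the 95% range is ±1.96 × 0.258 = ±0.51.
- Pr(|difference| > 0.1): 0.1/0.258 = 0.387, giving about 70%.
- With 71 patients in total (35.5 per arm): SE 0.237, giving about 67%.

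These probabilities are the same whether or not the RCSQ predicts opioid use.

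**4. False mediation.** Simulation of 20,000 trials per setting, 30 per arm, normal data, no treatment effect, RCSQ correlated r with the outcome (r is assumed). The effect SD is in outcome SDs, and the test requires both paths to have p < 0.05.

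| r | mean indirect effect | SD of indirect effect | joint test positive |
|---|---|---|---|
| 0.2 | 0.00 | 0.06 | 1.6% |
| 0.3 | 0.00 | 0.08 | 3.0% |
| 0.4 | 0.00 | 0.11 | 4.3% |
| 0.5 | 0.00 | 0.13 | 4.5% |

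A plain arm comparison of the RCSQ is significant in about 5% of trials, as expected under the null.

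**5. Gain from fixed adjustment.** Residual variance falls by r². The equivalent gain in patients is 1/(1 − r²) − 1.
- r = 0.2: 0.04/0.96 = 4%; power 84.0% → 85.5%.
- r = 0.3: 0.09/0.91 = 10%; power 84.0% → 87.3%.

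These figures ignore the cost of estimating the slope. In the simulation, the variance of the adjusted estimate relative to the unadjusted one was 1.02, 0.983 and 0.924 at r = 0, 0.2 and 0.3. That is a loss of about 2%, then gains of 1/0.983 − 1 = 2% and 1/0.924 − 1 = 8%.

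The imbalance rule already adjusts in about 70% of trials, so fixing the covariate adds something only in the other 30%. Very roughly, that is 0.3 × 4% = 1% and 0.3 × 10% = 3% on average.

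**6. Interaction.** With a median split of RCSQ, the interaction SE is 2 × 1.906 = 3.81. For an interaction as large as the whole assumed effect, 5.8/3.81 = 1.52, and power is about Pr(Z > 1.96 − 1.52) = 33%.

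**The case against.** The strongest reply is that no harmful analysis is actually written down. A reader might infer that the plan commits to an RCSQ mediation model or to an arm comparison of the RCSQ. The documents do not support that. Section 9.1 names no mediator, Section 9.2.3 specifies no mediation model, and the RCSQ line has no between-group wording, unlike the beverage line before it. The shared label suits beverages, which continue after the drug, and may simply have been repeated. This stands: the error is a wrong role label that could be acted on, not a specified faulty analysis.

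Nor does a chance SE of 0.26 mean that noise will be read as mediation. It is the ordinary sampling error of any baseline variable at this size, and the simulated false-positive rate stays below 5%.

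It is also fair to say that adjustment is not absent. The label includes confounding, and Section 9.2.2 gives a conditional route, though one that would apply to any baseline variable. What remains is that entry depends on chance imbalance and not on prognostic value.

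Finally, a reader might infer that modification by sleep is the trial's own rationale and that omitting an arm-by-RCSQ interaction is an error. The title of the cited rat study points that way, but Section 1.2 reports "protection against postoperative pain in both sleep-deprived and non-sleep-deprived rat models", which does not establish a differential effect, and the hypothesis in Section 1.3 mentions no sleep subgroup. At about 33% power, such a test could only be exploratory.

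**Conclusion.** The point holds in limited form. The tertiary-outcome listing and the mediator label are wrong for the RCSQ on the protocol's own timing, and any mediated effect found through it would be chance, at about 2% to 5% for r between 0.2 and 0.5. Its covariate role turns on a rule that chance meets in about 70% of trials at 30 per arm. The primary endpoint and the sample size are unaffected, so this is a modest but nearly free correction.

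The conclusion assumes intact randomisation and no selective loss of patients afterwards. The precision gain also depends on a correlation that the documents do not give: about 4% to 10% more effective patients at r = 0.2 to 0.3 before the slope cost, less on average given the existing rule, and a loss of about 2% if the RCSQ is unrelated to opioid use.

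**What to change.** - In Section 7.2, move the RCSQ out of the tertiary outcomes to a list of baseline variables and delete *mediating*.
- State that it is excluded from the mediator analyses in Section 9.1. If mediation through sleep is of interest, use the postoperative sleep-disturbance item.
- In Section 9.2.3, include continuous RCSQ as a pre-specified covariate in the regression of cumulative oral morphine equivalents, whatever its observed balance.
- State a simple imputation rule for a missing RCSQ, for example the overall mean taken without regard to arm, so that no patient is dropped. This matters because Section 9.2.2 allows complete-case analysis, and Section 3 warns that preoperative time limits may prevent some baseline cognitive testing. The warning is about the Trail Making Test, but the RCSQ is taken in the same setting.
- An arm-by-RCSQ interaction is optional. If kept, label it exploratory and report it with a 95% confidence interval.

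The cost is a change of wording and one degree of freedom. The RCSQ is already scheduled, so no new data are needed.
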